
complications amongst patients receiving dental implant therapy in a private practice setting.
	
and/or function of the implant restoration.
 
Incidence estimation will be based on a Poisson model for incidence per implant and year of follow-up.
	
and diameter, surgical therapy and site development, healing complications) and prosthetic data (type of restorations, abutment, restorative material, and occlusal scheme). At follow-up, practitioners will collect clinical data and record the presence or absence of the following complications on the prosthetics data collection survey: loose or lost screw, screw fracture, structural fracture, resin or porcelain fractures, loss of retention, abutment/implant misfit.
	
will be collected at the insertion of the prosthesis. The annual follow-up surveys at years 1-3 will record the presence or absence of prosthetic complications.

--	--	---	---

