- Clinical examination of the prosthesis: Screw fracture, Screw loosening, Loss of screw, Structural fracture, Resin fracture, Porcelain fracture, Loss of retention, Loss of filling covering screw, Abutment/implant misfit, Abutment/prosthesis misfit, Cement remnants present, Wear of the occlusal surfaces.
- Radiographs: Practitioners will submit digital radiographs of each study implant, taken at baseline (after implant prosthetic placement) and at annual follow-up visits 1, 2, and 3 years following prosthetic placement. The radiograph should be void of any identifiers. Radiographs will be uploaded to the centralized study database provided by the NCC. Node Coordinators will review the radiographs and remove identifiers if present. The study team completes the final review to determine whether the radiograph is sufficient quality to be included in the radiograph repository. If the radiograph is insufficient quality, the study team will work with the Node Coordinator to provide feedback, if applicable, and determine whether a higher quality radiograph can be found. Radiographs in the radiograph repository will go through the adjudication process, where trained and calibrated evaluators assess the radiograph for quality and will determine peri-implant bone height measurements and prosthetic fit for each implant.

Patients

Patient questionnaires will ascertain patient satisfaction and OHRQoL thought to be important patient-reported outcomes. Patient satisfaction with function and esthetics will be measured with the OHRQoL.

Baseline: At the implant prosthetic placement visit, patients will complete the *Baseline Patient Demographics, Patient Contact Survey, Patient Characteristics Survey and Baseline Oral Health Quality of Life (ORHQoL) Survey*, which will ascertain information related to: 1) demographics, 2) socioeconomic variables, 3) medication use, 4) medical conditions, 5) satisfaction with function and esthetics prior to implant therapy, and 6) oral health quality of life prior to prosthetic implant therapy.

Annual follow-up: Patients will complete the *1-, 2-, or 3-Year Patient Annual Follow-Up Survey, which includes the OHRQoL survey and Patient Contact survey*, to ascertain patient information related to: 1) Contact information changes 2) Changes in health history, medications and smoking habits, 2) OHRQoL following prosthetic implant therapy.

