For biologic complications, three binary outcomes will be examined: Peri-implant mucositis, Peri-implantitis and implant failure. For prosthetic complications, six binary outcomes will be examined including loosening of screws, screw fracture, structural fracture, resin or porcelain fractures, loss of retention, and abutment/ implant misfit. For the primary analysis, all outcomes will be defined at the person level and will be binary (Y/N) regardless of the number of complications experienced per participant. The 3-year cumulative incidence will be calculated as a ratio, where the numerator will be the total number of persons with one or more new (not existing at baseline) complications by the end of the follow-up period, and the denominator will be the total number of persons at risk for that complication at baseline. The prevalence will be calculated using the total number of persons with a complication (both new and existing) divided by the total number of persons at risk during each time interval (baseline, year 1, 2, and 3). In addition, the incidence and prevalence will be computed separately by age group, DM, smoking status, medication use, Osteoporosis, Radiation therapy, Periodontitis diagnosis, and Gingivitis diagnosis. We will calculate incidence and prevalence for all complications except implant failure (incidence only). If data permits, we'll also examine the number and rates of repeated prosthetic complications and the disease progression in biologic complications (mm bone loss over time) for exploratory analysis.

Secondary Objectives. To examine risk factors for biologic and prosthetic complications among patients receiving dental implant therapy in a private practice setting.

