The unit of analysis for the secondary objectives are at the implant level for the biologic complications and the prosthesis level for the prosthetic complications. All the outcomes are binary outcomes (Y/N), and for primary analysis only the first occurrence will be considered. Multiple implants/ prostheses are clustered within the same patient, and multiple patients clustered within practitioners. To account for these correlations, General Estimating Equations (GEE) will be used to identify practitioner, patient and implant variables that are associated with the complications. A binomial model with a logit link function will be used for these binary outcomes. Separate analyses will be conducted for each complication. The variables in table 3 will be considered as potential risk factors.

Secondary analysis will evaluate the association between patient/implant/prosthetic risk factors and the rates of repeated prosthetic complications and the disease progression in biologic complications. For the rates of prosthetic complications, the outcome will be the number (count) of prosthetic complications during the 3-year follow-up period. The unit of analysis will be at the person level, and Poisson models will be used to identify practitioner, patient and prosthesis risk factors that are associated with a higher rate of prosthetic complications. For disease progression in biologic complications, the outcome will be mm bone loss (continuous) over time. Mixed effects model will be used to

account for the longitudinal nature of the data and to identify the practitioner, patient and implant risk factors that are associated with a higher amount of bone loss.

Table 3.

Practitioner level factors	
Number of implants restored per month	biologic and prosthetic complications
Years in practice	biologic and prosthetic complications
Post graduate education	biologic and prosthetic complications
Specialty training	biologic and prosthetic complications
Patient level risk factor	outcome
Age at baseline	biologic and prosthetic complications
Diabetes Mellitus	biologic complications
Smoking status	biologic complications
Medication use SSRI Bone sparing drugs Corticosteroid use	biologic complications
Osteoporosis	biologic complications
Radiation therapy	biologic complications
Periodontitis diagnosis	biologic complications
Gingivitis diagnosis	biologic complications
Parafunctional habits	prosthetic complications
Implant/ Prosthesis level risk factor	

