Bone Grafting at time of implant placement	biologic complications
Immediate loading	biologic complications
Reason for tooth loss: Periodontitis	biologic complications
Reason for tooth loss: Endodontic failure	biologic complications
Reason for tooth loss: Caries	biologic complications
Reason for tooth loss: Trauma	biologic complications
Congenitally missing	biologic complications
Removable prosthesis	biologic complications
Poor prosthetic fit	biologic complications
Emergence angle	biologic complications
Cement remnants present	biologic complications
Open contacts present	biologic complications
Single tooth restoration	biologic and prosthetic complications
Multiple unit restoration splinted	biologic and prosthetic complications

Cemented restoration	biologic and prosthetic complications
Custom abutment	biologic and prosthetic complications
Stock abutment	biologic and prosthetic complications
Removable prosthesis full arch	prosthetic complications
Removable prosthesis: poor retention	prosthetic complications
Screw retained prosthesis	prosthetic complications
Opposing dentition: Natural	prosthetic complications
Opposing dentition: Complete denture	prosthetic complications
Opposing dentition: Partial denture	prosthetic complications
Occlusion: Mutually protected	prosthetic complications
Occlusion: Group function	prosthetic complications
Prosthesis material: Porcelain	prosthetic complications
Prosthesis material: Zirconia	prosthetic complications
Prosthesis material: Plastic	prosthetic complications
Prosthesis material: Zirconia with Porcelain veneer	prosthetic complications

Tertiary (exploratory) Objectives. To explore the OHRQoL (Oral Health-Related Quality of Life) following implant therapy, and to explore patient/implant/therapy level factors associated with patient satisfaction and OHRQoL.

The data from the OHRQoL will be used to quantify overall satisfaction with implant therapy and quality of life post-implant therapy, and will be presented at each time point to explore any potential time trend. In addition to baseline demographics and clinical factors, the type and location of prosthesis as well as the different types of complications will be included in correlation analysis with the OHRQoL survey data (Table 2). Because the OHRQoL score is a continuous variable, mixed effects model will be used to examine the association between these patient/implant/therapy factors and the OHRQoL score to account for the longitudinal nature of the data.

Table 4.

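### Prosthesis material is tested as a risk factor for a fracture outcome that is itself defined by material, so the material rows of two secondary models cannot show which material fractures more often

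*Protocol*

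**What the plan says.** **Outcome.** Protocol Section 3.1 lists the prosthetic complications recorded at follow-up as "loose or lost screw, screw fracture, structural fracture, resin or porcelain fractures, loss of retention, abutment/implant misfit". Section 11.3 makes them six binary outcomes, among them "structural fracture, resin or porcelain fractures, loss of retention, and abutment/ implant misfit". The clinical examination in Section 7.1 lists "Structural fracture, Resin fracture, Porcelain fracture, Loss of retention" as items. No item names zirconia, and the text does not say what counts as structural.

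**Model.** For the secondary objectives Section 11.3 works at the prosthesis level: "A binomial model with a logit link function will be used for these binary outcomes", and "Separate analyses will be conducted for each complication".

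**Risk factors.** Section 11.3 adds that "The variables in table 3 will be considered as potential risk factors". Table 3 has four material rows: Porcelain, "Prosthesis material: Zirconia", Plastic, and a further row for zirconia veneered with porcelain. Each is assigned to prosthetic complications as a whole, and no outcome is excepted.

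**The concern.** Table 3 gives veneered zirconia its own row, so the plain zirconia row reads as zirconia without porcelain. A prosthesis in that row contains neither of the materials that name the resin/porcelain outcome. The exposure then partly decides whether the outcome can occur at all, and the regression returns that definition as if it were a finding.

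If such a prosthesis breaks or chips, structural fracture is the only other listed item that fits. Events moved there make zirconia look worse in the structural-fracture model. The two models could therefore label the same material protective and harmful when its true fracture risk equals that of porcelain. Section 2.2 says the results should help practitioners with treatment decisions, and choice of material is one of them.

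**Working it through.** No figure stated in the protocol depends on this point, so there is nothing to reproduce. The check gives porcelain and unveneered zirconia the same true fracture risk and asks what odds ratio (OR) the outcome wording produces. The correct answer is 1.

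**Inputs.** The outcome list, the one-model-per-complication rule, the logit link and the material rows come from Sections 3.1, 7.1 and 11.3. The two-sided 0.05 level is from Section 11.3. Everything else is assumed: true 3-year fracture risk r of 5%, 10% or 16% in both materials, 400 prostheses per material, and the recording shares below.

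**1. Literal reading.** Zirconia has no events. With 40/400 in porcelain and 0/400 in zirconia, a test GEE gave an intercept of -2.197, which is ln(40/360), and a log OR of about -26. That is separation. The software still printed a standard error of about 0.25 for the log OR, so the output can look like a precise estimate.

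**2. Loose recording.** Suppose all porcelain-prosthesis fractures are recorded as resin/porcelain, and a share s of zirconia fractures is ticked there too. Then

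OR = [rs/(1 - rs)] / [r/(1 - r)].

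At r = 10% and s = 25%: (0.025/0.975) / (0.10/0.90) = 0.0256/0.1111 = 0.23.

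The table gives the OR for zirconia v porcelain. In brackets is the probability of a falsely significant difference, treating the prostheses as independent.

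| r | s = 10% | s = 25% | s = 50% |
|---|---|---|---|
| 5% | 0.10 (97%) | 0.24 (86%) | 0.49 (46%) |
| 10% | 0.09 (>99%) | 0.23 (99%) | 0.47 (77%) |
| 16% | 0.09 (>99%) | 0.22 (>99%) | 0.46 (94%) |

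The bias shrinks as recording becomes more alike. If 80% of the fractures of both materials are ticked as resin/porcelain, the OR is 1.

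**3. Structural fracture.** Suppose 20% of porcelain-prosthesis fractures but all zirconia fractures are recorded as structural. Then

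OR = [r/(1 - r)] / [0.2r/(1 - 0.2r)].

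- r = 5%: 0.05263/0.01010 = 5.2
- r = 10%: 0.11111/0.02041 = 5.4
- r = 16%: 0.19048/0.03306 = 5.8

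**4. Combined outcome.** If any of the structural, resin or porcelain items counts as an event, both materials have risk r and the OR is 1, whichever item was ticked. This needs the fracture to be recorded under one of the three. If 20% of zirconia fractures were recorded nowhere, then at r = 10% the OR would be (0.08/0.92) / (0.10/0.90) = 0.0870/0.1111 = 0.78.

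**The case against.** The strongest reply is that the split follows the mode of failure, not the material. The background in Section 2.1 separates framework fracture from chipping or fracture of the veneer, and the structural and resin/porcelain outcomes may map onto those two. On that view unveneered zirconia has no veneer to chip, and its breakage belongs under structural fracture. The reading is plausible, but the text does not state it, and it leaves the analysis problem in place. A model that compares materials on an event one of them cannot have does not measure comparative fracture risk.

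Section 11.3 also only says that the Table 3 variables will be considered. Coding and restriction of the models may be settled in the statistical analysis plan, which is not at hand, and the survey forms in the appendices might define the items. This is fair, and it limits the point. Still, the protocol itself sets the outcome list, the material rows and one model per complication, and together they create the built-in association.

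A Poisson model for the number of prosthetic complications is planned too. Its count does not depend on which fracture item was ticked. It works at person level and includes events other than fractures, so it answers only part of the question.

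A reader might go further and infer that zirconia fractures are missing from the primary incidence. The documents do not support this. Structural fracture stands in the same list and may capture them, and Hypothesis 2 concerns at least one prosthetic complication of any kind. The incidence denominator in Section 11.3 is limited to persons at risk for the complication in question, which may exclude patients with neither resin nor porcelain. A dilution figure that keeps everyone in the denominator therefore has no basis in the text.

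**Conclusion.** The point holds for the material rows of two secondary risk-factor models, resin/porcelain fracture and structural fracture. In neither does the zirconia coefficient show which material fractures more often. The incidences of these two outcomes also need care: neither, taken alone, should be read as the incidence of fracture of the restorative material in general. The incidence of any prosthetic complication is little affected, provided zirconia fractures are recorded under some item. Hypotheses 3 and 4 concern prosthesis type (screw-retained or cemented) and not material.

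Under the assumed equal risks, the false OR runs from zero on the literal reading to about 0.5 when half of zirconia fractures are ticked as resin/porcelain. In the structural model it is about 5 to 6 under the recording pattern assumed there. These values show direction and scale. They rest on assumed risks, group sizes and recording habits, and the false-positive probabilities ignore clustering. That zirconia has exactly zero events is a consequence of reading the item label literally and is not an established fact about the data. The effect by definition concerns unveneered zirconia only, since veneered zirconia can have the event.

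**What to change.** 1. In Section 11.3, test the four material rows of Table 3 against a combined outcome, any fracture of the prosthesis, met when the structural, resin or porcelain item is ticked. Screw fracture stays separate.
2. For the separate resin/porcelain model, either do not interpret material or restrict the model to prostheses that contain resin or porcelain. The restriction takes plain zirconia out of that comparison.
3. In Section 7.1, state under which existing item a fracture or chip of unveneered zirconia is recorded.

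The cost is wording in two sections. The combined outcome uses items already recorded and does not depend on which of them was ticked, so it also serves visits already completed. A new survey option is not needed. Section 5.5.2 suggests that the study is already running, and a changed item could make later visits differ from earlier ones. The downside is that the combined outcome mixes framework fractures with chips, so its components should still be reported descriptively.

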3.2 Secondary

Objective	Brief Description/Justification of Outcome Measure	Outcome Measured By	Time Frame

Determine risk factors for biologic complications amongst patients receiving dental implant therapy in a private practice setting.
	
Baseline risk factor data collection will include patient specific data, surgical data, and prosthetic data. Follow-up data will collect changes in implant health (biological complications).
 
Biologic complication measurements taken for the Primary Objectives will be used in the model for detection of risk factors.
 
Precision for detection of predictors of complications and
	
Patient data (patient age, gender, overall health, medications taken, oral health, periodontal disease status etc.), surgical data (described above) and prosthetic data (described above) BoP, gingival health data, and
	
Data are collected at baseline and at the 1-3-year annual follow-up visits and combined with the BoP and radiographic data.

	
correlates of patient satisfaction will be based on effect magnitudes that would be detectable.
	
radiographs will be collected.
	

Determine risk factors for prosthetic complications amongst patients receiving dental implant therapy in a private practice setting.
	
The risk factors for prosthetic complications can be estimated from a model created with the data collected at the baseline and follow-up data collection timepoints. Baseline data collection will include patient specific data, surgical data, prosthetic data; follow-up data will focus on the prosthetic performance (including prosthetic complications, described in Primary Objective above).
 
Precision for detection of predictors of complications and correlates of patient satisfaction will be based on effect magnitudes that would be detectable.
	
The practitioners will complete the specific data collection forms for patient data, surgical data and prosthetic data described above.
	
Data are collected at baseline and at the 1-3-year annual follow-up visit.


Assess patient Oral Health-Related Quality of Life (OHRQoL) and satisfaction with esthetics and function following implant therapy.
	
Patient centered outcomes are an important aspect of the overall outcomes of treatment. The patients' satisfaction with the esthetics, health and function will be collected by patient surveys. Changes in the overall OHRQoL and patient satisfaction will be reported.
	
Patients will complete OHRQoL surveys at baseline and follow-up visits. For patient satisfaction, surveys will be administered describing esthetics, function and health prior to the insertion of the implant prosthesis (baseline) and after insertion (follow-up).
	
The patient survey instruments are completed by the patients prior to insertion of the prosthesis, and at the 1-3-year follow-up visits.

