- The baseline data collection will occur at the prosthetic placement visit, at which time patient baseline characteristics, their overall health and oral health status will be collected, and peri-implant hard and soft tissue status and prosthesis data will be captured. Patients will undergo annual follow-up visits at 1, 2, and 3 years (with a preferred target window for each visit ranging from a target date of -30 days to +150 days of the visit following prosthetic placement). During or after follow-up visits, patients will report satisfaction with aesthetics and function and oral health quality of life measures. Reminder emails or texts, if the patient opts into text messaging will be sent to patients who do not complete the surveys. Practitioners will record data on the patients' oral health, peri-implant tissue health, and the implant prosthesis(es), with a focus on biologic and prosthetic complications that have occurred since prosthetic placement.

- Consent will be recorded electronically, and data will be collected via electronic means for the entire study. The consent process and enrollment will be completed at the prosthetic placement visit. Practitioners will provide clinical examination and procedural data electronically via tablets, smart-phones, or computers in-office or post visit at baseline and the 1-, 2-, and 3-year annual follow-up visits. Patient-reported data will be collected via tablets, smart-phones, or computers after in-office visits. To assist with in-office data collection, study practitioners may be offered tablets.
- Dental radiographs of each implant obtained for clinical care purposes will be collected at the following 4 time points: 1) baseline at the prosthetic placement visit, 2) 1-year annual follow-up visit, 3) 2-year annual follow-up visit, and 4) 3-year annual follow-up visit. Radiographs will be digitally uploaded via the study portal.

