14.3 Informed Consent Process

Patients: Participating practices will designate who will execute consent procedures for the study. In most cases this will be the participating dentist. Any personnel who will be assigned to obtain consent will be defined as study personnel and must complete required IRB training. Consent procedures will be administered prior to performing any study-related assessments or procedures.

The patient's consenting process will be initiated via a conversation with the practitioner, pursuant to the overseeing IRB requirements. The practitioner or designee will explain the research study to the patient, answer any questions that may arise, and discuss risks and possible benefits of study participation, if applicable. If required by the responsible IRB, an electronic or paper consent form describing in detail the study procedures and risks will be given to the patient to read and review the document or have the document read to him or her. The participant will e-sign the consent document or give verbal approval of the consent process (depending upon central or regional IRB requirements), and a copy of the consent document will be emailed or given to the patient for his/her records if applicable. The consent process will be documented in the research record. Patients may withdraw consent at any time throughout the course of the study.

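### The protocol times the baseline OHRQoL and satisfaction survey inconsistently (before insertion, at the placement visit, or after the visit), so the baseline may mix prospective and recalled answers

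*Protocol*

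**What the plan says.** Section 3.2 of the protocol lists patient OHRQoL and satisfaction with esthetics and function as a secondary objective. Its time frame reads: "The patient survey instruments are completed by the patients prior to insertion of the prosthesis, and at the 1-3-year follow-up visits". Its measurement column says that "surveys will be administered describing esthetics, function and health prior to the insertion of the implant prosthesis (baseline) and after insertion (follow-up"). The result it promises is a change: "Changes in the overall OHRQoL and patient satisfaction will be reported".

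Section 4 describes collection for the whole study: "Patient-reported data will be collected via tablets, smart-phones, or computers after in-office visits". The same bullet adds: "To assist with in-office data collection, study practitioners may be offered tablets". It also fixes when patients enter the study: "The consent process and enrollment will be completed at the prosthetic placement visit". Section 14.3 adds: "Consent procedures will be administered prior to performing any study-related assessments or procedures".

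Section 6.3 lists the baseline OHRQoL survey among the patient's tasks once enrollment procedures are done at the insertion visit. Section 7.1 has patients complete it at that visit. It describes the content as satisfaction before implant therapy and "oral health quality of life prior to prosthetic implant therapy". Appendix A lists the survey under Visit 1, Day 0. None of these three places orders the survey relative to insertion.

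**The concern.** The baseline score anchors the reported change. Before the prosthesis is seated, a patient describes a current or very recent state. After the visit, the patient has the new prosthesis in the mouth and has to recall the earlier state. These are different measurements, open to different errors: a recalled baseline carries risks of recall bias and response shift that a prospective one does not.

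About 200 practices will run the study. An office that follows Section 3.2 and one that follows Section 4 would each be acting on protocol text, yet they would deliver different kinds of baseline. The protocol describes no item that tells the two apart afterwards, and a pre-insertion answer cannot be recovered once the prosthesis is in place.

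**Working it through.** The protocol gives no sample size, standard deviation or expected effect for OHRQoL, so there is no figure to reproduce. The check is a comparison of the text.

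**Step 1: the timings side by side.**

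| Protocol section | Timing of the baseline patient survey | Order relative to insertion |
|---|---|---|
| 3.2, time frame | Before insertion | Before |
| 4, data collection bullet | After in-office visits, no baseline exception | After, if applied to Day 0 |
| 6.3 | At the insertion visit, after enrollment | Not stated |
| 7.1, patient baseline | At the placement visit | Not stated |
| Appendix A | Visit 1, Day 0 | Not stated |

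**Step 2: the available window.** Consent and enrollment take place at the placement visit (Section 4), and no study assessment may come before consent (Section 14.3). A survey that satisfies Section 3.2 therefore fits only between consent and seating on Day 0. A survey collected after that visit falls outside the window, so Sections 3.2 and 4 cannot both be followed at baseline.

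**Step 3: does another section settle the order?** No. Section 7.1 does order the practitioner's baseline forms, which follow the oral examination and placement of the prosthesis. It gives no such rule for the patient's forms.

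**Step 4: the state that the items ask about.** Section 7.1 uses two reference periods: before implant therapy for satisfaction, and before prosthetic implant therapy for OHRQoL. Section 3.2 refers to the time before insertion, and its wording can mean either when the survey is given or the state it describes. Under Section 5.2 the implants have already healed at enrollment. A question about the time before implant therapy therefore looks back past the implant surgery, even when it is answered before seating. The reference periods need aligning as well as the timing.

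**Step 5: can the bias be sized?** Let f be the share of patients who answer after insertion, and k the fraction of the true change already present in their baseline score. Then

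observed mean change = true mean change × (1 − f × k).

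The protocol gives neither f nor k. As an illustration only, with assumed f from 0.25 to 1 and k from 0.1 to 0.5, the understatement runs from 0.25 × 0.1 = 2.5% to 1 × 0.5 = 50%. If patients report the earlier state accurately, as the Section 7.1 items ask, k is near 0 and so is the bias. If they remember that state as worse than it was, k is negative and the change is overstated. The formula shows only that size and sign are undetermined.

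**The case against.** The best defense is that the sentence in Section 4 is a general statement about the mode of collection across all visits. The sections that deal with baseline specifically (3.2, 6.3 and 7.1) put the survey before insertion or at the visit, and Section 4 itself foresees tablets in the office. On that reading, sensible offices would collect the baseline on site. This lowers the likelihood of late surveys but does not remove the conflict: the tablets are optional, and a tablet survey at the end of the visit still comes after insertion.

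The second defense is that the items ask about the earlier state, so a late answer is not a score of the new prosthesis. That is correct. It rules out treating a late baseline as a follow-up value, but it leaves a recalled baseline mixed with prospective ones.

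A reader might infer three stronger things that the documents do not support:

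- **That the change is contaminated.** The protocol permits late baselines but does not show that they occur, or that their share differs between practices.
- **That a definite share of the true change is lost.** Any such figure needs values for f and k that the protocol does not contain.
- **That predictors of change cannot be trusted.** Sections 3.3 and 11.3 describe associations with the OHRQoL score over time, not an analysis of predictors of change. The three annual follow-up scores are untouched by the baseline timing.

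A last argument is that the handling of late surveys belongs in the statistical analysis plan, which is not at hand. That is fair for the analysis rule. It does not cover when the survey is given, which the protocol itself fixes in conflicting ways.

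**Conclusion.** The protocol contradicts itself on when the baseline OHRQoL and satisfaction survey is completed, and no section resolves the order on Day 0. An office following Section 4 as written would obtain a recalled, post-insertion baseline. The baseline may therefore mix prospective and recalled answers, and the change promised in Section 3.2 may be biased by an amount and in a direction that cannot be derived from the protocol.

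The exposure is limited to a descriptive secondary result, plus the baseline time point wherever that score is presented or modeled. The primary objectives on biologic and prosthetic complications do not use these data. The conclusion assumes only that the Section 4 sentence, which makes no exception, can be read as covering baseline. It does not assume that any late survey has been collected.

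**What to change.** 1. Reconcile Sections 3.2, 4, 6.3 and 7.1 so that the baseline patient survey is completed after consent and before the prosthesis is seated. Limit the after-visit wording in Section 4 to the follow-up visits.
2. Use one reference period for the baseline items in Sections 3.2 and 7.1, and check that the survey form carries the same wording.
3. Record for each baseline survey whether it was completed before placement (yes/no). The electronic survey time can serve instead where it establishes the order; a date alone cannot, since consent, survey and placement share Day 0. For any baselines already collected, use the survey times where they are informative and otherwise class the order as unknown.
4. Flag late surveys rather than discarding them. Report the change in OHRQoL and satisfaction with all baselines and again with confirmed pre-insertion baselines only, and prespecify which is the main analysis. Setting every late survey to missing is heavier than the problem warrants, because the items ask about the earlier state and the excluded patients may not be a random subset.

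The cost is an edit to the protocol text, one extra data item or a check of survey times, and a smaller sample in the restricted analysis.
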